## 9.3.2 Efficacy Analysis

FAS and PPS are both used for efficacy analysis, and of which, PPS is the main analysis set and FAS analysis can provide supporting evidence.

Analysis method of the primary efficacy endpoint: summary of BICR-assessed objective response rate (ORR) after administration according to RECIST1.1. The secondary endpoints include investigator-assessed ORR, BICR-assessed ORR according to irRECIST, progression-free survival (PFS), time to tumor progression (TTP), disease control rate (DCR), duration of response (DoR), survival rate at fixed time points (6, 9, 12 months) and overall survival (OS).

For the objective response rate (ORR), the point estimate, p-value of one-sided test and its 95% confidence interval (95% CI) will be provided. Kaplan-Meier method was used to estimate the survival functions for time to tumor progression (TTP), progression-free survival (PFS), and overall survival (OS), respectively, and their survival curves plots, the median TTP, median PFS, Survival rate at fixed time points and their respective 95% confidence intervals (95% CI) will be provided.

See the statistical analysis plan (SAP) for the details of Statistical Analysis.

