#### **Efficacy Assessment**

#### **Primary Efficacy Endpoint:**

Objective response rate (ORR) is the primary efficacy endpoint for both phase I and II, as assessed by investigator (Phase I) and Blinded Independent Central Review (BICR) (Phase II) according to RECIST 1.1 respectively.

ORR is defined as the proportion of enrolled subjects whose best response is CR or PR. Subjects assessed as CR or PR initially are required to be confirmed at the interval of at least 4 weeks.

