#### **Secondary Efficacy Endpoints:**

Phase I: irRECIST-based ORR.

Phase II: secondary efficacy endpoints of phase II study include:

BICR-assessed ORR according to irRECIST; Investigator-assessed ORRs according to RECIST 1.1 and irRECIST respectively;

Disease control rate (DCR): defined as the proportion of enrolled subjects with best response of CR, PR or SD assessed using RECIST 1.1 and irRECIST criteria respectively.

Time to tumor progression (TTP): defined as the time from the first administration to the time of radiographic disease progression under RECIST 1.1 and irRECIST criteria. Subjects without documented

radiographic progression due to loss to follow-up or changing treatment regimen during follow-up will be censored on the last radiographic follow-up date on which no disease progression is confirmed.

Duration of response (DoR): defined as the time from radiographic response to disease progression or death in subjects whose best response is CR or PR. DoR is assessed with RECIST 1.1 and irRECIST criteria respectively

Progression-free survival (PFS): defined as the time from the first dose to the date of tumor progression or death due to any cause. Disease progression is assessed using RECIST 1.1 and irRECIST criteria respectively. Subjects without documented radiographic progression or death during follow-up will be censored on the last follow-up date on which no disease progression is confirmed. For subjects without progression till the date of analysis, they will be censored on the last tumor assessment date.

Overall survival (OS): defined as the time from first administration to death caused by any reason. Subjects who are alive during the follow-up or are lost to follow-up without documented death will be censored on their last known alive date. For subjects alive till the date of analysis, they will be censored on their last known alive date.

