- 4. Analysis and sampling of biomarkers: a. Serum cytokines, receptor occupancy [only in dose escalation study], cell subset and markers prior to administration of MGD013; b. serum cytokines, receptor occupancy [only in dose escalation study], cell subset and markers prior to administration; c. for analysis of serum cytokinesand receptor occupancy [only in dose escalation study], samples will be collected prior to administration of MGD013 and after the completion of infusion respectively; for analysis of cell subset and markers, samples will be collected prior to administration of MGD013; d. for analysis of serum cytokinesand receptor occupancy [only in dose escalation study], samples will be collected prior to administration of MGD013 and after the completion of infusion; for analysis of cell subset and markers, samples will be collected prior to administration of MGD013. In addition, for subjects with immune- and infusion-related reactions or cytokine release syndrome, additional sampling for analysis of serum cytokinesmay be performed.
- 5. MRI can only be performed in subjects who are clinically suspected of central nervous system metastasis in the screening and subsequent periods. If the subject is contradicted to MRI, cranial CT can be performed.
- 6. Radiographic tumor assessments (contrast-enhanced CT of the chest, enhanced CT/MRI of the abdomen and pelvis at baseline, and subsequent contrast-enhanced CT/MRI of the abdomen and pelvis and clinically indicated sites) will be performed prior to treatment (baseline) using the same radiologic imaging modalities and will be repeated every 8 weeks throughout the study, with contrast enhancement required if not medically contraindicated. Subjects who discontinued from the study due to study drug toxicity or for any reason other than unequivocal tumor progression continued to undergo tumor assessment every 8 weeks during survival follow-up until disease progression confirmed or death. Subjects radiologically assessed as CR or PR for the first time should undergo confirmation of efficacy at the interval of at least 4 weeks.

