# 3.2.3 Selection of Efficacy Endpoints

The primary efficacy endpoint of the phase II study was objective response rate (ORR) according to RECIST 1.1. Secondary endpoints included ORR, TTP, PFS, OS, etc. according to irRECIST for immunotherapy, which could provide supportive evidence for clinical benefit.

Current radiologic evaluation criteria that can be applied to HCC include RECIST 1.1 criteria, mRECIST criteria, and irRECIST criteria for immunotherapy. Primary phase III clinical studies of immunotherapy in HCC adopted the RECIST 1.1 criteria (e.g., Checkmate-040 study, study of Atezolizumab in combination with Bevacizumab). The mRECIST criteria have not been fully validated for immunotherapy. Therefore, the ORR assessed according to RECIST 1.1 criteria was used as the primary efficacy endpoint for comparing with other studies. Provided that the characteristics of immunotherapy have been fully considered and a better rationality than RECIST 1.1 in terms of subject management (e.g., discontinuation of investigational drugs after reaching PD), it should be subject to irRECIST in case of investigator-assessed progressive disease and discontinuation of the investigational drugs.

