# 6.4 Post-Treatment Assessments (Subjects in phase II are not required to have visits in the study site)

- Subjects will receive survival follow-up and subsequent treatment follow-up to collect
  - the information (including commencement date of subsequent first anti-tumor treatment) of first anti-tumor treatment (including chemotherapy) after the end of study treatment every 60 days (± 7 days)
  - Subjects will receive survival follow-up after discontinuation of study treatment every 60 days (± 7 days) to collect the information of new malignant tumors
- Monitoring of SAEs and irAEs: study treatment-related SAEs or irAEs ≥ grade 3 occurring within 30 days after the last dose should be recorded and evaluated.
- Tumor imaging assessments and serum AFP: If the subject is withdrawn from the treatment for reasons other than radiographic progression, the subject will still need to undergo imaging scans and AFP testing every 8 weeks (± 1 week) after discontinuation of study treatment until tumor progression is confirmed or subsequent antineoplastic therapy is initiated

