## 7.2 Efficacy assessments

Contrast-enhanced CT or MRI of abdomen, pelvic and contrast-enhanced CT of lungs are required at baseline. During the follow-up visit, the same method of radiologic assessment on abdomen, pelvic cavity and other clinically indicated sites should be used. All baseline tumor imaging assessments must be performed within 28 days prior to the start of study medication. If subjects receive scanning before signing an informed consent form, as long as the scanning imaging is within the time limit specified by the protocol, the test method meets the requirements for image collection, and the data are obtained, it can be used for study analysis.

Radiologic examination should be conducted on abdomen, pelvic cavity and other clinically indicated sites every 8 weeks (±7 days) dated from the first day of the first cycle until disease progression. All imaging of Phase II study must be evaluated by independent central review.

Tumor assessment should be carried out in strict accordance with the study plan. If imaging assessment occurs beyond the planned visits and there is no disease progression, subsequent tumor assessments should still be carried out **according to the original plan**.

The investigator will also evaluate imaging response by RECIST 1.1 and irRECIST criteria, and classify the objective tumor response by target lesion assessment into: CR, PR, SD, PD and NE. For the subjects with initial response as PR or CR, the response should be confirmed at an interval of at least 4 weeks. subjects should be administered until PD confirmed according to irRECIST.

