## 9. Statistical Analysis

## 9.1 Analysis Set

Statistical analysis is performed using full analysis set (FAS), per-protocol set (PPS) and safety set (SS).

FAS: it includes all subjects who have received at least one dose of the investigational drug and have measurable tumors at baseline.

PPS: it includes subjects with at least one post-treatment imaging assessment of tumors, good compliance, and no serious violation or deviation against the study protocol in FAS population.

SS: it includes subjects who have received at least one dose of the investigational drug and undergone safety assessment.

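### The main analysis set for ORR and DCR drops treated subjects who were never scanned after baseline, although the plan defines both endpoints over enrolled subjects

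*Combined protocol and SAP*

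**What the plan says.** Section 9.3.2 and the Efficacy Analysis part of the synopsis use both the FAS and the PPS, and rank them: "PPS is the main analysis set and FAS analysis can provide supporting evidence". Neither place makes an exception for ORR or DCR. BICR-assessed ORR by RECIST 1.1, the Phase II primary endpoint, is therefore reported mainly on the PPS, with its one-sided p-value and 95% CI.

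Section 9.1 and the synopsis define the two sets:

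- **FAS:** at least one dose of study drug and measurable tumour at baseline.
- **PPS:** within the FAS, "it includes subjects with at least one post-treatment imaging assessment of tumors, good compliance, and no serious violation or deviation".

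The synopsis defines the endpoints over a different population. For the primary endpoint, "ORR is defined as the proportion of enrolled subjects whose best response is CR or PR". DCR is likewise "defined as the proportion of enrolled subjects with best response of CR, PR or SD". Section 9 gives no denominator of its own.

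Section 7.2 schedules imaging every 8 weeks (±7 days), "dated from the first day of the first cycle until disease progression". Table 1, footnote 6, adds that subjects who discontinue "due to study drug toxicity or for any reason other than unequivocal tumor progression continued to undergo tumor assessment every 8 weeks". Section 6.4 continues imaging after treatment stops "until tumor progression is confirmed or subsequent antineoplastic therapy is initiated", and Section 4.3.1 is similar.

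**The concern.** A treated subject without a post-baseline scan is a treatment failure for a response endpoint. Early death, withdrawal of consent, loss to follow-up and an early switch to other therapy can all produce such a subject. Under the synopsis definitions the subject counts in the denominator. Under Sections 9.1 and 9.3.2 the subject is removed. PPS membership thus depends on what happens after treatment starts.

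Phase II has no control arm to share the bias, so the choice of denominator feeds directly into the reported ORR, its interval and its p-value. Section 3.2.3 says RECIST 1.1 ORR "was used as the primary efficacy endpoint for comparing with other studies", and Section 1.1.2 quotes second-line ORRs of 14% and 17% for two PD-1 antibodies. A shift of one to two points is not negligible beside a three-point gap between those figures.

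**Working it through.** **1. The plan's own figures.** Section 9.2 and the synopsis allow 10% dropout. 30/0.9 = 33.3, rounded up to 34. 40/0.9 = 44.4, rounded up to 45. 2 × (34 + 45) = 158, the stated Part 1 maximum. Part 2 is planned at 120. The null and target ORR, alpha and power are not visible in the text, so the 30 and 40 themselves cannot be re-derived.

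**2. Direction of the bias.** Let *d* be the share of the FAS left out of the PPS. If all those left out are non-responders, PPS ORR = FAS ORR/(1 − *d*).

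- For subjects with no scan, that condition is true by definition, so the bias is upward.
- For compliance or deviation exclusions, a responder could be removed, so the bias is upward in expectation but not with certainty.
- Subjects who stop for toxicity but continue 8-weekly imaging are not lost through the scan criterion.

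**3. Plausible size of *d*.** The documents do not give it. I take 2.5% to 10% as an assumption. For scale, the 12-month survival figures in Section 1.1.2 (60% and 54%), under an assumed constant hazard, give deaths by week 8 of 1 − 0.60^(56/365.25) = 7.5% and 1 − 0.54^(56/365.25) = 9.0%. The 12-week life-expectancy criterion would lower these.

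**4. Effect at the Part 2 size.** The count of 24 responders among 120 treated is illustrative; intervals are exact (Clopper-Pearson).

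| *d* | Responders/N | ORR | 95% CI |
|---|---|---|---|
| 0 (FAS) | 24/120 | 20.0% | 13.3–28.3 |
| 2.5% | 24/117 | 20.5% | 13.6–29.0 |
| 5% | 24/114 | 21.1% | 14.0–29.7 |
| 10% | 24/108 | 22.2% | 14.8–31.2 |

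**5. Effect at the Part 1 sizes.** This assumes that every enrolled subject is treated and only the evaluable number enters the PPS. It is the upper end, because dropout is only a proxy for PPS exclusion. Responder counts are illustrative.

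- After checkpoint inhibitor: 6/34 = 17.6% becomes 6/30 = 20.0%.
- Checkpoint-inhibitor-naive: 7/45 = 15.6% becomes 7/40 = 17.5%.
- DCR moves the same way: 15/34 = 44.1% becomes 15/30 = 50.0%.

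**6. Effect on the one-sided test.** This is hypothetical, since the null rate, alpha and *d* are all assumed. With 120 treated and a true all-treated rate equal to the null p0, the number in the PPS is Binomial(120, 1 − *d*), the response rate within it is p0/(1 − *d*), and the PPS is tested exactly against p0. Actual type I error at nominal 5%:

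| p0 | FAS | *d* = 2.5% | *d* = 5% | *d* = 10% |
|---|---|---|---|---|
| 5% | 3.84% | 3.85% | 4.11% | 6.79% |
| 10% | 2.97% | 5.18% | 5.53% | 8.16% |
| 15% | 3.20% | 5.23% | 6.35% | 10.42% |

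At nominal 2.5% and p0 = 10%, the values are 1.58%, 2.32%, 2.93% and 4.47%. The FAS column lies below nominal because the exact test is conservative, so the fair comparison is with the nominal level. At 2.5% exclusion the error is near or below nominal. At 10% it exceeds nominal in every case shown.

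**The case against.** The strongest reply has four parts.

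- **The FAS result will be produced anyway.** This is true, so no information is lost. However, the plan labels it supportive, and the question is which ORR is primary.
- **The design is framed in evaluable subjects.** The stage-1 rules, the 30 and 40, and the rule of 6 responders in 30 all count evaluable subjects, so a PPS-type main set looks consistent with them. But those are accrual and go/no-go rules. The only definition of an evaluable subject (Section 3.1.1) concerns the Phase I DLT period, so its equivalence to the PPS is not established. It remains true that a FAS-based headline would use a different N from the decision rules, and the text should say so.
- **The contradiction may be loose wording.** The enrolled-subjects phrase appears only in the synopsis, and the FAS is not literally all enrolled subjects either. Since inclusion criterion 4 requires measurable disease, the FAS is essentially all treated subjects and much closer to the definition than the PPS. Section 9.3.2 also defers detail to an SAP. No separate SAP text is visible, so a correction there cannot be excluded, but the protocol wording would still conflict.
- **The effect is small and the comparators fit only partly.** Both points stand. At 2.5% to 5% exclusion the ORR moves 0.5 to 1.1 points. The quoted 14% and 17% are relevant only to the checkpoint-inhibitor-naive group.

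These points limit the size of the problem. They do not change its existence or direction.

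**Conclusion.** The concern holds. Followed as written, the plan removes treated subjects with no post-baseline scan from the primary denominator of a single-arm phase, against its own endpoint definitions, and that criterion can bias ORR and DCR only upward. The likely size is about 0.5 to 2.2 points on an ORR of 20%, for an assumed exclusion of 2.5% to 10% with no responders among those excluded. Any type I error inflation depends on a null and alpha that the text does not show: it is negligible at 2.5% exclusion and material at 10%. This should be fixed, but it does not undermine the design. The conclusion rests on the protocol text supplied.

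**What to change.** In Section 9.3.2 and the synopsis:

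- Make the FAS the primary set for ORR and DCR.
- State that FAS subjects with no post-baseline assessment, or no evaluable one, count as non-responders for ORR and as not controlled for DCR.
- Keep the PPS as a sensitivity analysis, and report the number excluded from it by reason.
- Align the denominator wording in the synopsis endpoint definitions with Section 9, and note that the stage-1 and 6-responder rules continue to count evaluable subjects. No change to those rules is proposed here.

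The cost is a wording change in the protocol and SAP. Both sets are already defined and no new data are needed. The reported ORR will be slightly less favourable.

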## 10. Clinical Trial Management

#### 10.1 Statement

This clinical study shall be implemented and reported in accordance with the *Declaration of Helsinki*, Chinese Good Clinical Practice, ICH GCP and local appropriate regulations.

#### 10.2 Ethical Considerations

Before initiating a trial, the investigator should obtain approval from the Institutional Review Board/Independent Ethics Committee (IRB/IEC) for the trial protocol, informed consent form and any other written information to be provided to subjects.

Before initiation of the clinical trial, approval must be obtained from the Ethics Committee. The approval issued by the Ethics Committee shall be made available to the investigator in written form. The investigator is obligated to provide the sponsor of a copy of the approval. The Ethics Committee approval should clearly list all the committee members involved in the review with their respective responsibilities.

During the clinical study, any of issues related to the subject safety of the clinical study, such as changes in the clinical study protocol or subject informed consent form as well as serious adverse events in the clinical study, must be reported to the Ethics Committee in a timely manner. The completion or termination of the clinical study must also be reported to the Ethics Committee.

#### 10.3 Source Data Verification

The investigator must properly handle all the data obtained during the clinical study, so as to ensure the rights and privacy of the subjects participating in the clinical study. The investigator must permit the monitor/auditor/inspector to consult and review required clinical study data to verify accuracy of original data and learn about study progress. If the original records cannot be verified, the investigator should agree to assist to further validation of data with them.

#### 10.4 Quality Assurance and Auditing

The quality of all drugs and materials used in the clinical study must be controlled. The sponsor, personnel authorized by the sponsor or related medical management institutions have the right to audit the clinical study in order to ensure the authenticity of the clinical study data and abide by the provisions of the clinical study protocol. Subjects participating in the clinical study will be informed of the audit, but the privacy and data of subjects will be strictly protected.

#### 10.5 Informed consent form

The investigator has the responsibility to explain to each subject the purpose, methods, benefits and potential risks of this clinical study. Signed informed consent must be obtained before conducting any study-specific procedures. Informed consent should be expressed in written form. The informed consent must be dated and signed by the subject him/herself. For those subjects who could not sign the informed consent form by themselves for any reasons, their parents, legal guardians, or protectors should sign the informed consent form. The original signed informed consent form and the process of obtaining informed consent should be preserved and documented in the case report form and relevant trial source documents by the investigator.

By signing the informed consent form, the subject must also agree to allow the sponsor, the drug approval authorities, and the auditor and (or) the monitor to check and verify the

obtained source data and materials related to clinical study, and all parties mentioned above must comply with confidentiality statement.

#### 10.6 Protocol Amendment

Upon finalization of the study protocol, any changes to the protocol must be filed in details, which should be at least jointly signed and dated by the investigator and the sponsor, with version numbers indicated.

The changes should involve the sponsor and the investigator. The revised contents should not be implemented before obtaining the approval of the Ethics Committee.

## 10.7 Case Report Form (CRF)

The CRO working on behalf of Zailab is responsible for data management, so as to ensure the authenticity, integrity, privacy and traceability of the clinical study data.

Information has been entered by the investigator and its authorized personnel to the eCRF, and only the investigator with a physician qualification certificate can sign on the clinical/safety evaluation conclusion. Any changes to the eCRF will be automatically recorded in the system after the input of source data.

#### 10.8 Monitoring

The Sponsor will designate a monitor for on-site monitoring. Monitors should operate in compliance with the company's standard operation procedure (SOP). They should perform regular visits from the start to the end of study.

The monitors will have access to relevant source data of the clinical study, and review CRF according to SOP to confirm information completeness, accuracy and consistency with original data.

CRFs, copies of lab tests and medical tests must be accessible to clinical monitors, auditors and health authorities for review at any time. Monitors should review all CRFs and informed consent forms.

